Added a new sentence “The reasons for preventative FIX/FVIII replacement	To clarify that the reasons for preventative infusions will now be captured and this will be done in eCRF.	Section SOA footnote g; Section 6.2 Baseline Visit; Section 6.3 Data Collection

Description of Change	Brief Rationale	Section # and Name
therapy will be captured in eCRF.”		Section 6.5 End of Study/Early Termination
Reworded text to clarify what AE events are reported on the CRF and SAE form within the table under AE reporting requirement section.	To clarify what events need to be recorded on CRF as well on SAE form.	Section 8.1 AE Reporting Requirements
Added updated text from April 2023 protocol template where applicable.	To align with current protocol template language version April 2023 to ensure regulatory compliance.	Section 10 (QUALITY CONTROL AND QUALITY ASSURANCE); Section 11.1, 11.3 (DATA HANDLING AND RECORD KEEPING); Section 12 (ETHICS); Section 15.1, 15.2 (PUBLICATION OF STUDY RESULTS)
Added “QTL” to abbreviation table in Appendix 1. Added FVIIa to abbreviation table in Appendix 1.	To align with updated QTL text and definition from Section 10. To clarify definition of acronyms.	Appendix 1
Added “New Untreated Bleed” definition to Appendix 2 to align with language in the SAP.	Minor clarifications for consistency with the SAP.	Appendix 2
Incorporated an administrative change from the protocol administrative change letter (PACL#15) dated 22 November 2022.	To clarify the definition of a bleed that necessitates administration of coagulation factor within 72 hours of signs and symptoms of bleeding is referred to as a “treated bleed”.	Appendix 2

TABLE OF CONTENTS

LIST OF FIGURES	10
APPENDICES	11

SCHEDULE OF ACTIVITIES.....	12
1. INTRODUCTION	15
1.1. Mechanism of Action/Indication.....	15
1.2. Background and Rationale	15
2. STUDY OBJECTIVES AND ENDPOINTS.....	17
3. STUDY DESIGN.....	18
4. PARTICIPANT ELIGIBILITY CRITERIA.....	19
4.1. Inclusion Criteria.....	19
4.2. Exclusion Criteria.....	20
4.3. Sponsor's Qualified Medical Personnel.....	23
4.4. Screen Failures	24
5. STUDY TREATMENTS.....	24
5.1. Allocation to Treatment	24
5.2. Participant Compliance	24
5.3. FIX or FVIII Replacement Therapy Supplies	25
5.3.1. Dosage Form(s) and Packaging	25
5.3.2. FIX or FVIII Replacement Therapy Storage	25
5.4. Concomitant Treatment(s).....	25
6. STUDY PROCEDURES	26

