Appendix 2. Bleed and Factor Replacement Regimen Definitions^{1,2,3}

Definition of a Bleed (for analysis purposes)

Treated Bleed: An event necessitating administration of coagulation factor within 72 hours of signs or symptoms of bleeding (protocol definition, unless specifically referring to untreated bleed).

Untreated Bleed: A bleeding event not necessitating administration of coagulation factor within 72 hours of signs or symptoms of bleeding.

New Treated Bleed: A treated bleed occurring >72 hours after stopping treatment from the original bleed for which treatment was initiated or a treated bleed occurring at a different site from the original bleed regardless of the time from last injection.

New Untreated Bleed: An untreated bleed occurring >72 hours after the previous untreated bleed at the same site or occurring >72 hours after stopping treatment from the original bleed for which treatment was initiated, or an untreated bleed occurring at a different site from the original bleed regardless of the time from last bleed or last injection.

Definition of a Bleed Location

Target Joint: Defined as a major joint (eg, hip, elbow, wrist, shoulder, knee, and ankle) into which repeated bleeds occur (three or more spontaneous bleeds into a single joint within a consecutive 6-month period). A target joint is considered resolved when there are ≤ 2 bleeds into the joint within a 12-month period.

Joint Bleed: A bleeding episode characterized by rapid loss of range of motion as compared with baseline that is associated with any combination of the following: pain or an unusual sensation in the joint, palpable swelling, and warmth of the skin over the joint.

Muscle Bleed: An episode of bleeding into a muscle, determined clinically and/or by imaging studies, generally associated with pain and/or swelling and functional impairment.

Definition of Bleed Types

Spontaneous Bleeds: Bleeding for no apparent/known reason particularly into the joints, muscles, and soft tissues.

Traumatic Bleeds: Bleeding event occurring for an apparent/known reason.

Note: Bleeds related to a procedure/surgery such as hematomas/bruising resulting from any surgeries or invasive procedures (eg, tooth extractions, venipuncture, or subcutaneous drug administrations) or invasive diagnostic procedures (eg, lumbar puncture, endoscopy with biopsy) would NOT be counted as bleeds. Bleeds related to procedure/surgery are not associated with any trauma except procedure/surgery-induced trauma.

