3. ENDPOINTS AND BASELINE VARIABLES: DEFINITIONS AND CONVENTIONS

3.1. Primary Endpoint(s)

The primary endpoint is ABR (treated and total). A bleeding episode is defined in Protocol Appendix 2.

If a bleed is treated with FIX infusion (for Hemophilia B) or FVIII infusion (for Hemophilia A) (according to Bleeding eDiary or Bleeding CRF) within 72 hours post the start of bleeding (by comparing date/time of bleeding to date/time of infusion in Infusion eDiary or Infusion CRF), regardless of the type of treatment (preventive, prophylaxis or rescue medication), it will be considered as a treated bleed. If a bleed is not treated with FIX/FVIII infusion according to the Bleeding eDiary or the Bleeding CRF, the bleed will not be considered as a treated bleed but considered as an untreated bleed.

If there are multiple concurrent bleeds (spontaneous or traumatic) on the same date AND time but in different locations in a participant, they will be recorded as one bleed for that participant. If concurrent bleeds occurred on the same day but at different times and different locations, they will be counted as separate bleeds. Only new bleeds (as defined in Protocol Appendix 2) will be counted toward the number of bleeds for ABR calculation.

For untreated bleed, every occurrence will be counted as a separate bleed.

The ABR per participant based on prospectively collected bleeds will be calculated as:

The number of bleeds (all treated bleeding episodes including spontaneous and traumatic) x 365.25 days/number of days during the observation time period while the participant received prophylaxis factor replacement therapy in the usual care setting from baseline visit (Day 1) to end of study (date of study completion or discontinuation, whichever is earlier).

Number of bleeds (treated bleeds and all bleeds, respectively) and infusions within the last 12 months will be collected at the screening visit using hemophilia history CRF for all participants enrolled under Protocol Amendment 5 (01 Oct 2020) or under a subsequent protocol amendment. Thus the retrospectively collected ABR per participant will be equal to number of bleeds in the past 12 months collected in the Hemophilia History form.

Participants enrolled in hemophilia A cohort or hemophilia B cohort prior to Protocol Amendment 5 will not have the CRF retrospectively filled out.

ABR combining retrospective and prospective data will be calculated as:

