3.2. Secondary Endpoint(s)

The AIR per participant will be calculated as:

The number of infusions received x 365.25 days/number of days during the observation time period while participant received prophylaxis factor replacement therapy in the usual care setting from baseline visit (Day 1) to end of study (date of study completion or discontinuation, whichever is earlier).

Similarly as ABR (Section 3.1), the retrospectively collected AIR per participant will be equal to number of infusions within the last 12 months collected in the Hemophilia History form.

AIR combining retrospective and prospective data will be calculated as:

$$\frac{(\text{Number of infusions from baseline visit (Day 1) to end of study} + \text{Number of infusions collected in Hemophilia History form})}{(\text{Number of days from baseline visit (Day 1) to end of study} + 365.25)/365.25}$$

The annualized factor consumption will be calculated as:

The total factor replacement therapy consumption (in international unit [IU] and dose) x 365.25 days/number of days during the observation time period while the participant received factor prophylaxis replacement therapy in the usual care setting from baseline visit (Day 1) to end of study.

The number of bleeding episodes will be annualized using the same methods as the primary endpoint by spontaneous, traumatic and overall (treated and untreated) as defined in Protocol Appendix 2.

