6. ANALYSES AND SUMMARIES

6.1. Primary Endpoint(s)

6.1.1. Annualized Bleeding Rate

The primary endpoint listed in the protocol is the annualized bleeding rate (ABR; treated and total).

ABR during the prospective data collection period

Annualized bleeding rate during the prospective data collection period will be summarized using descriptive statistics (ie, n, mean, standard deviation, median, Q1, Q3, minimum, maximum) by cohort. The ABR will be summarized for the efficacy analysis set, the per-protocol analysis set, and the PA#5 analysis set.

ABR during the retrospective data collection period

Annualized bleeding rate during the retrospective data collection period will be summarized using descriptive statistics. The ABR will be summarized for the PA#5 analysis set.

ABR from the combined the retrospective and prospective data collection period

Annualized bleeding rate from the combined retrospective and prospective data collection period will be summarized using descriptive statistics. The ABR will be summarized for the PA#5 analysis set.

ABR will be listed in a data listing. For retrospectively collected data, the source of collection (medical records, diary log, or participant recall) will be presented.

The analyses will be provided for ABR of treated bleeds and ABR of all bleeds, respectively.

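### SAP 3.1 gives two conflicting rules for counting untreated bleeds, so total ABR has no single definition

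*SAP*

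**What the plan says.** SAP 3.1 defines the primary endpoint as ABR in two forms, treated and total. SAP 6.1.1 asks for both: "The analyses will be provided for ABR of treated bleeds and ABR of all bleeds, respectively".

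On counting, SAP 3.1 states "Only new bleeds (as defined in Protocol Appendix 2) will be counted toward the number of bleeds for ABR calculation". The statement that follows is "For untreated bleed, every occurrence will be counted as a separate bleed".

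Protocol Appendix 2 gives the bleed definitions to be used in analysis. The treated bleed is the default ("protocol definition, unless specifically referring to untreated bleed"), and there are separate definitions of a new treated and a new untreated bleed. The first limb of the latter is "An untreated bleed occurring >72 hours after the previous untreated bleed at the same site". The other limbs, joined by "or" in the text, cover a bleed more than 72 hours after treatment of the original bleed stopped, and a bleed at a different site. The summary of changes for Amendment 8 records adding this "definition to Appendix 2 to align with language in the SAP".

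SAP 3.2 carries the primary-endpoint method into the secondary bleed rates, to be reported "by spontaneous, traumatic and overall (treated and untreated) as defined in Protocol Appendix 2".

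**The concern.** The first counting sentence restricts every ABR count to Appendix 2 new bleeds and is not limited to treated bleeds. The second removes any such restriction for untreated bleeds. Appendix 2 does not count every untreated occurrence, so the two sentences give different totals whenever a participant records repeat untreated bleeds close together at one site.

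Two programmers could each follow SAP 3.1 and report different total ABRs from the same diary data. The exposed outputs are prospective total ABR, the prospective part of the combined retrospective and prospective total ABR, and the rates in SAP 3.2 and 6.2.2 wherever they include untreated bleeds. The study has no hypothesis test, but its data are collected for comparison with efficacy after gene therapy, so the descriptive figures need one definition.

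**Working it through.** The plan states no figure that depends on the untreated-bleed rule, so there is none to reproduce. The check applies both rules to the same hypothetical records.

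**Inputs.** SAP 3.1: ABR = bleeds × 365.25 / days. Protocol Appendix 2: the new treated and new untreated definitions. Assumed follow-up: 183 days (about 6 months), with 90 and 365.25 days for comparison.

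**1. Smallest example.** Two untreated bleeds at one site, 48 hours apart, no earlier treated bleed there.
- Appendix 2 counts 1: 1 × 365.25 / 183 = 2.00.
- Every occurrence counts 2: 2 × 365.25 / 183 = 3.99.

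**2. Effect of one extra record.**
- 90 days: 365.25 / 90 = 4.06 per year.
- 183 days: 365.25 / 183 = 2.00 per year.
- 365.25 days: 1.00 per year.

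**3. A longer hypothetical log over 183 days.** Two treated bleeds (elbow, ankle) and five untreated records. Three knee records fall within 60 hours of each other, one elbow record comes 36 hours after treatment there stopped, and one knee record comes much later. Appendix 2 counts the first and last knee records only.

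| | Treated | Untreated | Treated ABR | Untreated ABR | Total ABR |
|---|---|---|---|---|---|
| New bleeds only | 2 | 2 | 3.99 | 3.99 | 7.98 |
| Every occurrence | 2 | 5 | 3.99 | 9.98 | 13.97 |

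The log is built to show the mechanism; it does not predict the data. Treated ABR is the same in both rows because the new-treated definition makes no use of untreated bleeds.

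**4. Cohort mean, 183 days.** Rise in mean total ABR = share of participants with one extra record × 1.996. For assumed shares of 0%, 5% and 10%, the rise is 0, 0.10 and 0.20 bleeds per year.

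**5. Relative size.** Let u be the untreated share of the bleeds that Appendix 2 counts, and r the number of uncounted same-site repeats per counted untreated bleed. The relative rise in total ABR is u × r:
- 0.2 × 0 = 0%
- 0.2 × 0.1 = 2%
- 0.3 × 0.4 = 12%
- 0.5 × 0.5 = 25%

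The documents give neither u nor r; these values are assumptions.

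**6. Direction.** For same-site untreated bleeds, the every-occurrence count equals or exceeds the Appendix 2 count and is never lower. SAP 3.1 separately merges bleeds at the same date and time in different locations, which can lower counts relative to Appendix 2. The net direction of all departures from Appendix 2 is therefore not known.

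**The case against.** The best counter-reading treats the every-occurrence sentence as the specific rule for untreated bleeds and the new-bleeds sentence as the rule for treated ones. The ABR formula that follows refers to treated episodes, which lends this some support. Both documents let the SAP modify the protocol, and SAP 5.0 (19 September 2024) is later than Amendment 8 (31 March 2023) and records a change to this counting text. The later, more specific wording may therefore be what the sponsor wants.

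That does not remove the conflict. The SAP does not call the sentence an exception, and the preceding rule admits none. SAP 3.1 cites Appendix 2 as the controlling definition without limiting it to treated bleeds, and SAP 3.2 invokes both the primary-endpoint method and Appendix 2 for overall rates. If every occurrence is counted, the new-untreated definition has no use in counting.

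Four points on the other side stand:
- The Amendment 8 rationale is weak evidence of intent, because the SAP text it referred to is not supplied.
- Because Appendix 2 joins its conditions with "or", a repeat within 72 hours of an untreated bleed could still be new if treatment of an earlier bleed had stopped more than 72 hours before. That narrows the cases in which the rules differ. The examples above avoid it.
- The percentage range rests wholly on assumed inputs.
- Retrospective counts come from the Hemophilia History form and are unaffected.

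**Conclusion.** The concern holds as stated. For untreated bleeds at the same site, SAP 3.1 gives two incompatible counting rules and does not say which governs, so prospective total ABR and the untreated and overall rates lack a single definition.

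The secure part of the size is arithmetic: each disputed record moves a participant's total ABR by 2.00 per year at 183 days and 1.00 at 365.25 days. The effect at cohort level is unknown and may be zero; the 0% to 25% range holds only for the assumed values of u and r. This conflict leaves treated ABR, the protocol's default, unchanged. Its effect on the later gene-therapy comparison cannot be judged without the counting rules of C0371002 and C3731003, which are not supplied. It should be fixed, but it does not undermine the treated-bleed results.

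**What to change.** State one rule. The most direct change is to delete the every-occurrence sentence from SAP 3.1 and apply Appendix 2's new-untreated definition to total ABR and to the untreated and overall rates in SAP 3.1, 3.2, 6.1.1 and 6.2.2. The every-occurrence count can be kept as a labelled sensitivity analysis.

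If the sponsor intends every occurrence as the main rule, write it as an explicit exception to the preceding sentence and amend Appendix 2 to match. In either case, confirm that the rule is the one used in C0371002 and C3731003.

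The first option costs one SAP sentence and one programming rule, since bleed date, time and location are already collected; total ABR may come out slightly lower. The second also needs a protocol amendment to bring Appendix 2 into line.

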9.2.1. Analysis of the Primary Endpoint

The annualized bleeding rate (ABR) per participant will be calculated as the number of bleeds over number of days from baseline visit (Day 1) to end of study x 365.25 days. ABR will be summarized using descriptive statistics (n, mean, standard deviation, median, Q1, Q3, minimum, maximum).

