9.2.2. Analysis of Secondary Endpoints

The annualized infusion rate (AIR) per participant will be calculated as the number of infusions received over number of days from baseline visit (Day 1) to end of study x 365.25 days. AIR will be summarized using descriptive statistics (n, mean, standard deviation, median, Q1, Q3, minimum, maximum).

The total respective Factor IX or VIII replacement therapy consumption and the corresponding dose will be descriptively summarized by the categories of the replacement therapy, where appropriate. Infusion diary (electronic diary) of the respective Factor IX or VIII replacement therapy will be listed.

The number of bleeding episodes will be summed up by spontaneous, traumatic and overall, as defined in [Appendix 2](#).

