$$\frac{(\text{Number of bleeds from baseline visit (Day 1) to end of study} + \text{Number of bleeds collected in Hemophilia History form})}{(\text{Number of days from baseline visit (Day 1) to end of study} + 365.25)/365.25}$$

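### Does the on-prophylaxis clause in the SAP's day count make the ABR and AIR differ from the protocol's formulas?

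*SAP*

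**What the plan says.** **Formulas with the clause (SAP).**
- Prospective ABR, section 3.1: treated bleeds are annualized over the "days during the observation time period while the participant received prophylaxis factor replacement therapy in the usual care setting from baseline visit (Day 1"), ending at study completion or discontinuation, whichever comes first.
- Prospective AIR, section 3.2: the divisor is the "number of days during the observation time period while participant received prophylaxis factor replacement therapy in the usual care setting", with the same start and end.
- Annualized consumption, section 3.2: days are counted "while the participant received factor prophylaxis replacement therapy in the usual care setting from baseline visit" to end of study.
- ABR by bleed type (spontaneous, traumatic, overall) takes over the ABR method, also in section 3.2.

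**Formulas without it.**
- Protocol 9.2.1, ABR: "the number of bleeds over number of days from baseline visit (Day 1) to end of study x 365.25 days".
- Protocol 9.2.2, AIR: "the number of infusions received over number of days from baseline visit (Day 1) to end of study x 365.25 days".
- SAP 3.1, combined retrospective and prospective ABR: the prospective part of the divisor is "Number of days from baseline visit (Day 1) to end of study". The combined AIR in SAP 3.2 has the same divisor, and its numerator is the "Number of infusions from baseline visit (Day 1) to end of study" plus the infusions from the history form.

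Consumption has no competing formula. Protocol 9.2.2 says only this: "The total respective Factor IX or VIII replacement therapy consumption and the corresponding dose will be descriptively summarized". It does not annualize, and the SAP has no combined consumption rate.

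**The concern.** The clause sits in the divisor of the primary endpoint and is missing from the protocol's version of the same endpoint. Read as an instruction, it takes off-prophylaxis days out of the day count. The numerators (all treated bleeds, all infusions received) carry no matching restriction, so days would be lost while events were kept, and each affected rate would go up.

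Two things would be at stake. First, Protocol 1.2 says these data are the control for the gene therapy studies, and an inflated control ABR would flatter the comparison. Second, SAP 6.1.1 reports prospective and combined ABR side by side in the PA#5 analysis set, so one participant's two rates could rest on different day counts. Protocol Appendix 2 defines prophylaxis as a regimen, but neither document says what an off-prophylaxis day is.

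**Working it through.** The documents state no ABR, no AIR and no off-prophylaxis time, so there is no plan figure to reproduce. Every T, off-time, bleed count and participant share below is an assumption.

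**Step 1. Three readings.** Let T be days from Day 1 to end of study, f the share of T off prophylaxis, b all bleeds, and b_on the bleeds that occur on prophylaxis.
- A, clause describes the study period: b × 365.25 / T. This is the protocol formula.
- B, clause restricts days only: b × 365.25 / (T(1 − f)).
- C, clause restricts days and bleeds: b_on × 365.25 / (T(1 − f)).

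So B/A = 1/(1 − f) and C/A = (b_on/b)/(1 − f). At f = 0, b_on = b and all three coincide.

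**Step 2. Size of B against A.**
- f = 5%: 1/0.95 = 1.053. f = 10%: 1/0.90 = 1.111. f = 25%: 1/0.75 = 1.333.
- T = 183, 18 days off, 2 bleeds: A = 2 × 365.25/183 = 3.99; B = 2 × 365.25/165 = 4.43; ratio 183/165 = 1.109.
- Cohort mean, assuming equal underlying rates, is 1 + (share affected) × (ratio − 1). If 10% of participants have 18 of 183 days off: 1 + 0.10 × 0.109 = 1.011. If 25% have 45 days off (183/138 = 1.326): 1 + 0.25 × 0.326 = 1.082.

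**Step 3. The direction is not fixed.** Take T = 183, f = 25% (137.25 days on prophylaxis) and 2 bleeds.
- A = 3.99.
- B = 2 × 365.25/137.25 = 5.32.
- C with one bleed off prophylaxis = 1 × 365.25/137.25 = 2.66.
- C with both bleeds on prophylaxis = 5.32.

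The prospective numerators in SAP 3.1 and 3.2 have no start or end date of their own. The only dated window in each formula is the one attached to the day count, so events must already borrow it. If they borrow the dates, they can equally borrow the clause, which is reading C. Inflation is therefore a property of reading B alone.

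**Step 4. Can SAP 4.2 bound f?** Only in part. With more than 120 days of follow-up, a gap between consecutive infusion records above 25% of follow-up removes the participant from the efficacy set. At T = 183 the limit is 0.25 × 183 = 45.75 days, so 45 days (24.6%) stays in and 46 days (25.1%) goes out. That suggests 1/(1 − 0.25) = 1.33 for one gap. The rule does not reach a stretch before the first or after the last record, several shorter gaps, off-prophylaxis time that contains infusions, or follow-up of 120 days or less. It also treats a gap as poor documentation, not as time off therapy. It therefore gives no usable estimate of f.

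**Step 5. Which reading do the documents support?**
- Prophylaxis replacement therapy in usual care is how both documents describe the study throughout (Protocol 1.1, 1.2, 2 and 3; SAP 2.1 and 2.2).
- The clause is followed at once by explicit start and end points, the same window as in the protocol.
- Where the SAP intends an exclusion it gives numbers, as in section 4.2 (120 days, 25%). Here it gives none.
- The follow-up summary in SAP 6.5.2 has no on-prophylaxis version.
- Protocol 9 and SAP 2 both commit to a protocol amendment for any major change to the primary endpoint definition. SAP version 5.0 is tied to Amendment 8, whose section 9.2.1 has no such restriction.

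All five points favor reading A.

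**The case for a change.** The best case for a change is that words placed inside a divisor ought to mean something. The SAP does not say whether they describe or exclude, so two programmers could in principle report different primary results. Continuous prophylaxis is the intention but is not guaranteed: Protocol 5.3.1 lets regimens be adjusted for medical need, Protocol 5.4 allows bypassing or nonfactor agents by exception, and follow-up can be short. If the clause is only descriptive, deleting it costs nothing.

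The difference in wording stands, and so does the arithmetic for reading B. The rest carries less weight. A programmer who wanted to exclude days would find no rule for doing so. The design also leaves little to exclude: participants must intend to stay on prophylaxis throughout (Protocol 4.1), they remain on their usual regimen (Protocol 5), and compliance is reviewed at least monthly (Protocol 5.2). The exception in Protocol 5.4 does not say that prophylaxis stops. That deletion is cheap shows only that it would do no harm; under the natural reading it alters no result. Under the other readings the question becomes whether an all-days or an on-prophylaxis rate is the better summary, and statisticians may reasonably differ on that.

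**Conclusion.** No change to the plan follows. The SAP's prospective formulas carry a clause that the protocol and the combined formulas lack, but its natural meaning is the study period itself, and then every ABR and AIR formula uses the same days. The difference is zero on that reading, and also on any reading if participants stay on prophylaxis.

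Under a days-only exclusion a participant's rate would be multiplied by 1/(1 − f); under an exclusion of days and events it could move either way. Since f appears nowhere in the documents, the figures above are illustrations and not estimates. The study tests no hypothesis (SAP 5.1), and how the gene therapy studies compute their control rate is set out in plans not available here. The conclusion assumes that analysts take Day 1 to end of study as the window for both events and days, which is the only window the documents define. This is a looseness of wording that analysts can be expected to resolve sensibly.
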